1. SYNOPSIS

Study Title	A phase 3, open-label study to assess the clinical utility of fluciclovine (¹⁸ F) PET/CT in patients with prostate cancer with biochemical recurrence (BCR) after initial treatment	
Internal ref. no. / short title	Fluciclovine (¹⁸ F) PET/CT in biochemical AL reCurrence Of prostate ca N cer (FALCON); BED-004	
Study Design	This is a phase 3, open-label study to confirm the clinical benefit of fluciclovine (¹⁸ F) PET/CT in patients with biochemical recurrence of prostate cancer (BCR).	
Study Participants	Patients with BCR being considered for radical salvage treatment (with curative intent), having had primary radical curative therapy performed at least 3 months before enrolment.	
Planned Sample Size	Recruitment of 180 patients with anticipation of 171 patients completing the trial.	
Planned Study Period	Patients will be followed up for treatment outcome and standard of care investigation results for up to 7-8 months after completion of treatment plan. Duration on study will be up to 7-8 months after completion of treatment plan.	
	Objectives	Endpoints
Primary	To assess the clinical impact of fluciclovine (¹⁸ F) PET/CT in affecting management decisions in patients with BCR being considered for radical salvage treatment (with curative intent).	The record of the revised management plan post fluciclovine (¹⁸ F) PET/CT scan in comparison to the pre-scan intended management plan.
Secondary	
 To assess possible improvement in outcome of radical salvage treatment based on fluciclovine (¹⁸F) PET/CT being included in the assessment. To assess the prostate specific antigen (PSA) threshold for positive lesion detection by fluciclovine (¹⁸F) PET/CT in BCR To assess the safety of fluciclovine (¹⁸F) injection in patients undergoing PET/CT 	
 The proportion of patients who have a sustained response to radical salvage therapy. PSA levels in relation to scan positivity will be analysed to determine the optimal PSA threshold for detecting recurrent PCa by fluciclovine (¹⁸F) PET/CT. Safety will be assessed from data on the occurrence of adverse events (AEs) and changes in clinical laboratory tests, vital signs, injection-site status, and physical examination findings from the

		time of administration of fluciclovine (¹⁸ F) injection throughout the study period.
--	--	--

2. ABBREVIATIONS

AE	Adverse Event
CI	Chief Investigator
C.I.	Confidence Interval
CRF	Case Report Form
CT	Computed Tomography
CTCAE	Common Terminology Criteria for Adverse Events
GCP	Good Clinical Practice
GP	General Practitioner
ICF	Informed Consent Form
ICH	International Conference of Harmonisation
MRI	Magnetic Resonance Imaging
NHS	National Health Service
NRES	National Research Ethics Service
PET	Positron Emission Tomography
PI	Principal Investigator
PIL	Participant/ Patient Information Leaflet
R&D	NHS Trust R&D Department
REC	Research Ethics Committee
SOP	Standard Operating Procedure
SPECT	Single Photon Emission Computed Tomography
US	Ultrasound

3. BACKGROUND AND RATIONALE

Prostate cancer (PCa) is the commonest cancer in males in the UK, accounting for 25.9% of total malignancies in men in 2012, with an age-standardised incidence of 174.7 per 100,000 males [1]. It is the second commonest cause of male cancer deaths [2] with a recurrence rate of 20-30% in patients who have received primary radical treatment [3].

The diagnosis of PCa is often made following the detection of elevated prostate-specific antigen (PSA) and / or an abnormal digital rectal examination, with confirmation of diagnosis by prostate biopsy. PSA is used as a tumour marker and its levels are positively correlated with the risk of metastatic disease or subsequent disease progression.

The primary treatment of PCa can be divided into radical and non-radical treatment, the former applicable to patients with localised non-invasive disease. Radical primary treatment options include radical prostatectomy (RP), radical external beam radiotherapy (RRT) and brachytherapy. Following radical treatment, patients undergo surveillance via PSA measurement. Detection of PSA post radical therapy (at least 6 weeks post treatment in the case of RP), or an initially falling and then rising PSA are evidence of biochemical disease relapse, BCR. Depending on clinical factors and local practice, patients may undergo imaging, usually a bone scan and or pelvic MRI, to confirm the sites and extent of disease relapse.

3.1 Conventional Imaging in BCR

Standard imaging investigations are an isotope bone scan to evaluate for bony metastatic disease [4] and MRI / CT to assess for local / nodal recurrence [5]. However, BCR after RP or RRT precedes clinical metastases by 7-8 years on average, rendering the diagnostic yield low in asymptomatic patients [6]. EAU guidelines recommend these tests only be performed in patients with BCR who have a high baseline PSA (> 10 ng/mL) or a high PSA velocity (> 0.5 ng/mL/month) or in patients with symptoms of bone disease. The positive detection rate of these investigations are poor below these thresholds [7, 8]. In BCR patients with PSA ≤ 10 ng/ml, Dotan et al [9], only 4% of patients had positive bone scans. Studies have shown CT to be positive in only 11–14% of men with BCR after RP [8, 10]. The diagnosis of nodal involvement on conventional cross-sectional imaging (CT / MRI) is based primarily on nodal size, which is known to be inaccurate, with pooled sensitivities of 39% and 42% for MRI and CT respectively and pooled specificities of 82% in both modalities [11]. As such, the utility of imaging and type of investigation in BCR varies across the UK.

3.2 FDG PET-CT Imaging in BCR

The uptake of FDG is low in prostate cancer and its use as an imaging agent in PET-CT in prostate cancer has been shown to be of limited value [12, 13]. Several radionuclide tracers have been developed for clinical use in prostate cancer. The most well-established tracers in clinical use within Europe are choline-based PET radiotracers.

3.3 Choline PET/CT

The concept of using radiolabelled choline in the imaging of prostate cancer is based on the overexpression of choline kinase by prostate cancer cells, a property shared with other tumour types [14]. Two different forms of radiolabelled choline are in current use, ^{11}C -choline and ^{18}F -fluorocholine. With the latter, two chemically variant compounds are commercially available, ^{18}F -fluoromethylcholine and ^{18}F -fluoroethylcholine. No in vivo studies directly comparing the different forms of radiolabelled choline have been published.

Choline PET/CT has better diagnostic performance in detecting sites of recurrent prostate cancer than conventional imaging and ^{18}F -FDG PET/CT. Evangelista et al [15] pooled data from 2 studies (n=89) comparing ^{11}C -choline to ^{18}F -FDG PET/CT in detecting prostate cancer metastases. In ^{11}C -choline and ^{18}F -FDG PET/CT scans respectively, they reported pooled sensitivities of 65.1 % (95% C.I. 53.8–75.2 %) and 39.8 % (95% C.I. 29.2–51.1 %), and pooled specificities of 83.3 % (35.9–99.6 %) and 83.3 % (35.9–99.6 %). Von Eyben et al [16] pooled data from 7 studies (n=280) comparing choline PET/CT to bone scintigraphy. Choline PET/CT yielded positive results for more patients [127 (45%) vs. 46 (16%), odds ratio (OR) 2.8, 95% C.I. 1.9–4.1]. In a cohort of 109 BCR patients with negative conventional imaging (transrectal US, MRI, abdominopelvic CT, bone scintigraphy), Giovacchini et al reported positive ^{11}C -choline PET/CTs in 11% [17].

The adoption of choline PET/CT has also been shown to have clinical impact. In a recent retrospective multicenter study, Ceci et al [18] reported ^{11}C -choline PET/CT led to a major clinical impact change in management in 18% of patients, with an overall management change in 46.7%. Von Eyben et al 2014 pooled data from 15 studies (n=938) evaluating the impact of choline PET/CT on changing treatment in prostate cancer [16]. They reported 41% of patients undergoing a change in treatment. Based on a secondary pooled analysis restricting this cohort to patients with BCR [19-22], 40% underwent a change in treatment. Furthermore, patients with negative choline PET/CT results had better BCR-free, disease-free and treatment-free survival rates than those with positive findings. Choline PET/CT positivity/negativity was the only significant predictor of treatment-free survival.

In the same meta-analysis, PSA response following a change in treatment based on choline PET/CT results was evaluated using pooled data from 10 studies (n=404) [16]. This demonstrated 25% of patients having a complete PSA response. Treatments included salvage lymphadenectomy (LND) and pelvic radiotherapy.

Despite better diagnostic performance compared to conventional imaging, choline PET/CT still suffers from suboptimal sensitivity. Whenever choline-PET/CT identifies a suspected lesion, almost twice as many metastases are present [23], an observation reflected in data from recent meta-analyses. Von Eyben et al [16] pooled data from 11 studies (n=609) evaluating the performance of choline in detecting lymph node metastases in BCR – with histological correlation. Pooled sensitivity was 59% (51%–66%) and specificity was 92% (89%–94%). Hence, choline cannot adequately characterise the extent of nodal disease in BCR.

In the context of primary prostate cancer, Evangelista et al [24] pooled data from 10 studies (n=441) evaluating the performance of choline in detecting lymph node involvement. This also yielded a relatively poor pooled sensitivity of 49.2% (95% C.I., 39.9-58.4%), with a higher specificity of 95% (95% C.I., 92-97.1%).

While it performs better than conventional imaging counterparts, the detection rate of choline PET/CT remains poor in the setting of relatively low PSA and slow PSA kinetics. Husarik et al and Castellucci et al reported a moderate and low detection rate in case of PSA value <2 ng/mL and <1.5 ng/mL (71.4% and 28%), respectively [25, 26]. The detection rate of metastases has been described to range between 20% and 36% in patients with PSA <1 ng/mL, compared to 63%-83% where PSA levels exceed 3 ng/mL [27-29]. In a cohort of 109 BCR patients with negative conventional imaging (TRUS, MR, abdominopelvic CT, bone scintigraphy), Giovacchini et al reported a higher rate of positive ¹¹C-choline PET/CTs with higher PSA [17]. Imaging was positive in 3 of 65 (5%), 4 of 26 (15%) and 5 of 18 patients (28%) with PSA between 0.2 and 1, between 1 and 2, and greater than 2 ng/ml, respectively.

As with other diagnostic tests, choline PET/CT is liable to produce false positive findings. This is reflected in the aforementioned diagnostic performance parameters and has been described in a number of entities. These included increased choline uptake within: the prostate in benign prostatic hypertrophy (BPH) [30], lymph nodes due to inflammation [31, 32], the prostate bed due to post-surgical scarring and inflammation post-RP/RRT [33], bones due to degenerative change or recent fractures [34].

The two different forms of radiolabelled choline, ¹¹C-choline and ¹⁸F-fluorocholine, have individual drawbacks. ¹¹C-choline exhibits early accumulation in small bowel limiting pelvic analysis [35]. The short 20-minute half-life of ¹¹C limits the use of ¹¹C-choline to centres with an on-site cyclotron and radiopharmacy facilities. Its short half-life also limits the scope for obtaining delayed acquisitions to improve tumour-to-background ratio. The latter can be performed with ¹⁸F-fluorocholine, which has a longer half-life of 110 minutes. This also makes it a more widely distributable tracer. However, high urinary tract uptake and excretion of ¹⁸F-fluorocholine into the urinary bladder limits assessment of the prostate bed [36].

3.4 Conventional and Emerging Radical Salvage Options in BCR

The options for radical salvage therapy (with curative intent) in BCR remain controversial [5]. In the context of prior RP, the main option is salvage radiotherapy (SRT) to the prostate bed. In patients with intact prostates, having had prior primary RRT or brachytherapy, a wider range of options for salvage therapy with curative intent are available. These include salvage radical prostatectomy, salvage cryotherapy, salvage brachytherapy and salvage HIFU [5].

The described therapies are local treatments, directed at the prostate / prostate bed. Based on current mainstream practice, the presence of disease outside the prostate bed precludes radical salvage therapy. Paradoxically, current NICE guidelines recommend against the use of conventional imaging in patients being considered for radical salvage therapy [37], unless symptomatic. This may be rationalised by the observation of more favorable outcomes from radical salvage therapy at low PSA levels, particularly SRT [38], and foreknowledge of the poor diagnostic performance of conventional imaging at such PSA levels. While this in itself underpins the need for an imaging test to accurately detect extra-prostatic disease and thus prevent unnecessary radical salvage treatment, there is an emerging role for salvage treatment of limited nodal disease, with several reports of promising clinical endpoints based on early results. This has been described in the form of salvage pelvic lymphadenectomy (LND) or targeted pelvic radiotherapy, the latter afforded by the advent of more sophisticated techniques, namely intensity modulated radiotherapy (IMRT) and stereotactic beam radiotherapy (SBRT).

Rigatti et al [39] evaluated the effect of salvage LND in 72 patients with BCR post-RP, who had choline-positive lymph nodes on PET/CT. They reported a complete PSA response in 56.9% of patients and 5-year recurrence-free and cancer-specific survival of 24% and 75% respectively. The mean PSA in this cohort was 1.5 ng/ml. In 47 patients with BCR and a history of RP or RRT and choline-positive nodal disease, Jilg et al [40] evaluated the impact of salvage LND (with adjuvant radiotherapy in a subset). Similar outcomes were reported, a complete PSA response in 46% and 5-year recurrence-free and cancer-specific survival of 25.6% and 77.7% respectively.

Alongi et al [41] described an overall response rate of 82% (over a median follow-up of 195 days) to SBRT of isolated lymph node metastases in 34 patients with previously radically treated PCa. In a cohort of 24 patients with BCR and up to 3 synchronous bone or nodal metastases treated with SBRT, Berkovic et al [42] reported a median delay in commencing ADT of 38 months (95% C.I. 18–58 months). In another cohort of 34 patients with BCR and isolated disease recurrence (in various sites) on imaging, robotic SBRT resulted in a progression-free survival of over 40% at 30 months, and complete PSA response in over 60% treated with SBRT alone [43].

3.5 Rationale for accurate imaging in BCR

As mentioned previously, the presence of disease outside the prostate bed precludes radical salvage therapy based on mainstream practice. In addition, more favorable outcomes from salvage therapy are observed at low PSA levels [38], when the diagnostic performance of current imaging options is poor. Conversely, the presence of a high PSA is associated with an increased risk of metastatic disease [44], the presence of which precludes the option of radical salvage therapy. Herein lies the ongoing need for an imaging test to detect sites of recurrent disease earlier and with greater accuracy, to aid clinical management in patients with BCR.

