In the largest cohort to date of intra-individual comparison of fluciclovine (¹⁸F) to ¹¹C-choline PET/CT, Nanni et al compared diagnostic performance between the two tracers in 28 patients with BCR after RP, in a single-centre study [50]. In the setting of relatively low PSA levels (mean 2.9 ng/mL, range 0.2- 14.6), the positive detection rate was found to be higher in fluciclovine (¹⁸F) compared to ¹¹C-choline PET/CT (35.7% vs 17.8%). Specifically, the detection rate was higher at PSA levels ≤ 1 ng/mL and > 2 ng/mL, and similar at levels between 1 – 2 ng/mL. All choline-positive lesions were also fluciclovine-positive. Fluciclovine (¹⁸F) PET/CT was positive in an additional 5 patients who had negative ¹¹C-choline PET/CTs. The tumour-to-background ratio (TBR) of fluciclovine (¹⁸F) was greater than ¹¹C-choline in 83.3% of lesions. There were also fewer false positive findings on fluciclovine (¹⁸F) PET/CT. Increased choline uptake by liver angiomas and several inflammatory inguinal lymph nodes were fluciclovine-negative. The same trend of higher detection rates across all PSA levels, and higher TBR in fluciclovine (¹⁸F) PET/CT compared to ¹¹C-choline PET/CT in a larger cohort of 50 patients was more recently presented by the same group [51].

Compared to its radiolabelled choline counterparts, fluciclovine (¹⁸F) also has a more favourable biodistribution. It has minimal renal excretion and associated bladder activity, and low homogeneous activity in the bowel [52]. Furthermore, being an ¹⁸F labelled tracer, it is a distributable product which does not have to be manufactured on-site.

With a high positive predictive value (95.7%) for extra-prostatic disease, almost entirely confirmed by histology, and a higher detection rate than choline, fluciclovine (¹⁸F) bears hallmarks of a competitively diagnostic agent in BCR. The impact of fluciclovine (¹⁸F) PET/CT on clinical management of patients with BCR remains to be defined, as is the PSA level associated with probability of a positive scan. Furthermore, the encouraging results on diagnostic performance observed at two expert centres need to be corroborated with larger multi-centre data, in order to formally validate its clinical utility for medical practice.

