3.7 Proposed Research

In the setting of growing single-centre evidence of superior diagnostic performance of fluciclovine (¹⁸F) PET/CT in BCR, our primary aim is to assess its clinical impact on treatment decisions in a multi-centre study in patients with BCR being considered for radical salvage treatment (with curative intent). In addition, we aim to further characterise its diagnostic performance, afforded by larger numbers of patients from multi-centre recruitment. We also aim to assess the effect of PSA level on probability of lesion detection by fluciclovine (¹⁸F).

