4.4.3 Prostate Cancer History

Details of prostate cancer history will be summarised for subjects from the FAS, and will consist of:

- Time since initial diagnosis (months), calculated as [12*(date of informed consent date of initial prostate cancer diagnosis + 1)/365.25]
- TNM stage: Pathological TNM stage if available, otherwise Clinical TNM stage. A summary for T1 total, T2 total and T3 total will be provided as the sum of the number of subjects in each of the subgroups plus any subjects where only T1, T2 or T3 was recorded.
- Gleason total score: Gleason total score from surgery if available, otherwise Gleason total score from biopsy
- Time since adjuvant treatment (months), calculated as [12*(date of informed consent stop date of adjuvant treatment + 1)/365.25]
- Duration of adjuvant treatment (months), calculated as [12*(stop date of adjuvant treatment – start date of adjuvant treatment + 1)/365.25]

- Time since diagnosis of biochemical recurrence (days), calculated as (date of informed consent – date of diagnosis of biochemical recurrence + 1). Time since diagnosis of BCR may be derived in months if more appropriate.
- Baseline PSA value
- Baseline PSA category (0 0.2, >0.2 0.5, >0.5 1, >1 2, >2 5, >5 10 and >10)

In addition, summary table to summarise baseline Prostate Specific Antigen (PSA) by Prior Radical Prostatectomy status (Prior Radical Prostatectomy vs No Prior Radical Prostatectomy) using descriptive statistics (number of subjects (n), mean, standard deviation (SD), minimum, median, and maximum), will be produced.

Details of prostate cancer history will be listed.

Date imputation for incomplete dates:

- If day part missing, put 15th of the month
- If day and month parts missing, put 01 July

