5.4.2 Secondary Efficacy Analyses

5.4.2.1 Treatment response as assessed by change in PSA

An assessment of treatment response, which is based on the percentage change in PSA from baseline to the last value reported, is defined as:

- >=30% decrease in PSA will be considered to be a response to treatment
- <25% increase or <30% decrease will be classified as stable disease
- >=25% increase in PSA will be classified as disease progression

See section 2 General Principles for baseline definition.

The number, percentage and exact 95% CI of subjects having a treatment response, stable disease and disease progression, as assessed by change in PSA, will be presented overall and separately for subjects in the FAS who had salvage treatment, for subjects who had non-salvage treatment, for those with a change in management plan and for subjects with no change in management plan following the ¹⁸F-fluciclovine PET/CT scan. In addition, treatment response assessed by change in PSA will be summarised by disease location (local disease versus extra-prostatic disease) and treatment administered.

The percentage change in PSA from baseline to the last value reported will be summarised overall and by subjects who had a change in management plan versus those who did not have a change in management plan following the ¹⁸F-fluciclovine PET/CT scan, disease location and treatment administered.

Finally, a waterfall plot of the maximum percentage reduction in PSA during the 4-8 month window will be presented on the y-axis and each subject will be represented by a bar on the x-axis. The bars will be ordered in descending order of the magnitude of the percentage change in PSA value.

Treatment response and the factors used to assess the response will be listed in full.

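### The PSA-response contrasts by plan change and by fluciclovine guidance are open to confounding by pre-scan PSA and prior prostatectomy, which the response analyses do not use

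*Protocol*

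**What the plan says.** **PSA and outcome.** Protocol 3.5 states that "more favorable outcomes from salvage therapy are observed at low PSA levels [38], when the diagnostic performance of current imaging options is poor". Protocol 3.4 says the same, with emphasis on salvage radiotherapy. Protocol 3.5 adds that "the presence of a high PSA is associated with an increased risk of metastatic disease".

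**PSA and scan positivity.** Protocol 3.3 cites a choline cohort in which positivity was 3/65, 4/26 and 5/18 for PSA 0.2 to 1, 1 to 2 and above 2 ng/mL. For fluciclovine, Protocol 3.6 lists what still has to be defined and includes "as is the PSA level associated with probability of a positive scan". Protocol 3.7 makes this a study aim: "We also aim to assess the effect of PSA level on probability of lesion detection by" fluciclovine.

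**Prior prostatectomy.** Under Protocol 6.2, patients treated with radiotherapy or brachytherapy enter with PSA at least 2.0 ng/mL above nadir. Patients treated by prostatectomy can enter with a final PSA just above 0.1 ng/mL after two rises, provided the doubling time is at most 15 months or PSA is at least 1.0 ng/mL. Protocol 3.4 describes different salvage options for the two groups.

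**Response analyses.** SAP 5.4.2.1 classifies response by percentage change in PSA from baseline to the last value. It tabulates counts, percentages and exact 95% CIs overall, for salvage and non-salvage recipients, and "for those with a change in management plan and for subjects with no change in management plan". It also summarises by disease location and by treatment administered. Addendum 2, Change 1, adds response in salvage recipients by whether therapy was guided by fluciclovine. The stated reason is to assess improvement in salvage outcome from including the scan.

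**Where the two baseline variables are used.** PSA bands are an analysis factor only for the detection rate (SAP 5.4.2.2). Prostatectomy status splits the primary-endpoint summaries (SAP 5.4.1). SAP 4.4.3 adds a "summary table to summarise baseline Prostate Specific Antigen (PSA) by Prior Radical Prostatectomy status".

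**The concern.** A baseline variable that is related both to the grouping and to the outcome can create a difference between groups with no effect of the scan. The protocol asserts the outcome half for PSA in salvage recipients. The grouping half is plausible, because changing a plan or directing a boost depends on what the scan shows, and that may depend on PSA. Prior prostatectomy is tied to entry PSA by the eligibility rules and to the salvage treatments available.

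Every participant is scanned (Protocol 7.4), so no unscanned group exists against which to judge the secondary objective on salvage outcome. The within-trial contrasts are the only comparative material. The SAP words the plan-change summary as one group against the other, and Addendum 2 presents the guided table as serving that objective. A reader who takes the crude rates as evidence for or against the scan cannot separate its effect from the PSA and prostatectomy mix.

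**Working it through.** **1. The plan's own sizing.** The plan gives no figure for the response contrasts; its only sizing is for the primary endpoint. n = 1.96² × 0.20 × 0.80 / 0.06² = 170.7, so 171, and 171 / 0.95 = 180. Both reproduce. Protocol 11.3 reports that recruitment stopped after an interim look at 85 evaluable patients. The final number is not stated, so 85 and 180 serve as the range below.

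**2. Size of a spurious difference, two PSA levels (all values assumed).** With no effect within PSA level, crude difference = (response gap between PSA levels) × (gap in low-PSA share between groups).
- Response 80% at low and 50% at high PSA; low PSA in 30% of changed and 60% of unchanged plans.
- Changed: 0.3 × 0.80 + 0.7 × 0.50 = 0.59. Unchanged: 0.6 × 0.80 + 0.4 × 0.50 = 0.68. Difference −9 points.
- Smallest assumed gaps: 0.15 × 0.20 = 3 points. Largest: 0.30 × 0.40 = 12 points.
- If either gap is 0, the product is 0.

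**3. A version using the protocol's choline PSA mix.** The three PSA bands hold 65, 26 and 18 patients. Response by band is assumed, with no effect within bands.

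| Grouping | Response by band | Exposed | Unexposed | Difference |
|---|---|---|---|---|
| Choline positivity (3, 4, 5 exposed) | 80/70/60% | 8.2/12 = 68.3% | 72.8/97 = 75.1% | −6.7 |
| Same | 80/60/40% | 6.8/12 = 56.7% | 68.0/97 = 70.1% | −13.4 |
| Assumed change rate 40/55/70% | 80/70/60% | 38.37/52.9 = 72.5% | 42.63/56.1 = 76.0% | −3.5 |
| Same | 80/60/40% | 34.42/52.9 = 65.1% | 40.38/56.1 = 72.0% | −6.9 |
| Change rate flat, or response flat | any | equal | equal | 0 |

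Stratifying by PSA band returns 0 in every row. Step 3 borrows a choline gradient, so it shows the mechanism and does not estimate this trial.

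**4. Precision.** For 59% versus 68% in two equal groups, half-width = 1.96 × √[(0.59 × 0.41 + 0.68 × 0.32) / (N/2)].
- N = 85: 1.96 × √(0.4595 / 42.5) = 20 points.
- N = 180: 1.96 × √(0.4595 / 90) = 14 points.

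**5. Which strata can be populated.** The SAP's seven PSA bands by two groups give 85/14 ≈ 6 to 180/14 ≈ 13 per cell if evenly spread. Crossing PSA bands with prostatectomy is worse: the entry rule of 2.0 ng/mL above nadir leaves bands below 2 essentially empty in patients without prostatectomy. Three strata by two groups give 85/6 ≈ 14 to 180/6 = 30 per cell, and fewer once restricted to salvage recipients.

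**The case against.** The strongest reply has five parts.

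- **Descriptive only.** SAP 5.4.2.1 gives rates and per-group intervals with no test, and SAP 5.4.5 rules out subgroup analyses. This does not close the gap. The SAP already splits results by scan result, prostatectomy, location, treatment and Gleason score, and Addendum 2 puts such a table to a comparative purpose. The proposed addition is also descriptive.
- **PSA is already in the endpoint.** It enters as the denominator of percentage change, which does not balance prognosis between groups.
- **The causal chain is partly inferred.** This stands. A reader might infer that the protocol says PSA drives fluciclovine positivity, so the contrasts are confounded and scan-led changes will look worse than they are. The documents do not support that. The sentence in 3.5 concerns current imaging options, the cited gradient is choline's, and 3.6 leaves the fluciclovine relation open. SAP 5.4.1 tabulates change after negative as well as positive scans and has a category for moving to watchful waiting, so a positive scan need not be what changes a plan. The change/no-change summary also pools salvage and non-salvage treatment, which can move the crude difference either way.
- **PSA may mark disease extent.** This stands for local versus extra-prostatic disease, where adjusting for PSA could remove part of what is being described.
- **Low resolution and timing.** The illustrated 3 to 12 points lie inside the interval half-widths in step 4. Addendum 2 already documents additions after database lock, so a new table now would be post hoc. Both limit what the table can show. Neither makes the crude contrast safer to read.

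**Conclusion.** The point holds as a risk of confounding, not as demonstrated bias. The change/no-change contrast in SAP 5.4.2.1 and the guided/not-guided contrast in Addendum 2 leave out two baseline variables that are already collected. The protocol links PSA to salvage outcome and links prior prostatectomy to entry PSA and salvage options.

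The size and direction of any bias cannot be determined from the documents. The 3 to 12 point range rests on assumed response gaps of 15 to 30 points and assumed low-PSA gaps of 20 to 40 points, and falls to 0 if grouping is unrelated to PSA or response is flat across it. The primary endpoint is unaffected. The statement that neither variable is used refers to the visible text: the first SAP addendum and the table shells are not in the documents reviewed.

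**What to change.** 1. In SAP 5.4.2.1, add one table of PSA response among subjects who received salvage therapy, in three baseline strata: prior prostatectomy with lower pre-scan PSA, prior prostatectomy with higher pre-scan PSA, and no prior prostatectomy. Use one pre-stated cut from the SAP's own bands, for example 1.0 ng/mL. Take PSA from the general baseline in SAP 2 (last value before fluciclovine), because it precedes the plan decision.
2. Within salvage recipients, beside the crude change/no-change and guided/not-guided rates, give the Mantel-Haenszel difference Σw(p₁ − p₀)/Σw with w = n₁n₀/(n₁ + n₀) in each stratum, and its 95% CI. State how many subjects fall in strata with an empty group. Label the result descriptive, non-causal and, if added after database lock, post hoc.
3. For local versus extra-prostatic disease, show the baseline PSA distribution by group and do not adjust.

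Cost: SAP or addendum wording and one or two tables from data already held. Downsides: small strata, intervals at least as wide as those in step 4, residual confounding, and selection on a post-scan decision because the table is limited to salvage recipients. Under Protocol 6.2, patients after prostatectomy with PSA below 1.0 ng/mL at recruitment must have a doubling time of at most 15 months, so the lower-PSA stratum also differs in PSA kinetics; a footnote should say so.
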